8.4 Analysis Methods

8.4.1 General Principles

Quantitative data will be statistically described using mean, median, standard deviation, maximum, and minimum values. Categorical or ordinal data will be presented with frequency and percentage. Antibody levels for immunogenicity indicators will be expressed using geometric mean, median, maximum, minimum values, and 95% confidence intervals. Antibody levels will undergo log transformation for statistical analysis.

All statistical analyses will be conducted using SAS software version 9.4 or higher.

8.4.2 Cellular Immunogenicity

For both the experimental vaccine group and the active control vaccine group, the proportion of gE-specific CD4+ T cell and CD8+ T cell activation with at least two cytokines (IFN- γ , TNF- α , IL-2, CD40L) at 30 days post-full immunization will be calculated along with their 95% confidence intervals (using the Clopper-Pearson method). The difference in proportions between the experimental vaccine group and the active control group and its 95% confidence interval (using the Miettinen and Nurminen method) will also be calculated. If the lower limit of the 95% confidence interval for the difference is greater than -10%, non-inferiority is established. Cellular immunogenicity analysis will primarily be based on the per-protocol set.

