3.1.1 Sample Collection

3.1.1.1 Blood sample collection

Blood samples will be collected from all subjects once before vaccination and once 30 days after full immunization, for a total of two blood samples. The ELISA method will be used to measure varicella-zoster virus (VZV) gE-specific antibodies, and flow cytometry will be used to assess VZV gE-specific CD4+/CD8+ T cell activation. The proportion of subjects activating at least two cytokines (TNF- α , IFN- γ , IL-2, CD40L) will be calculated to evaluate the vaccine humoral and cellular immune response. Detailed blood sample collection time points, volumes, and purposes are shown in the table below:

Visit Time	Test items and blood collection volume (ml)		
	Serum Antibody	Cellular Immune	Total
D0	4.0-5.0	15.0-20.0	19.0-25.0
30 days after full immunization	4.0-5.0	15.0-20.0	19.0-25.0

Note: Serum antibody testing is performed using procoagulant tubes for blood collection; cellular immunity indicators are tested using anticoagulant tubes for blood collection.

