3.2.3.1 Phase I clinical trial

The Phase I clinical trial in healthy individuals aged 50-70 years was conducted with a 0 and 1month immunization schedule, administering one dose of the experimental vaccine or placebo to the deltoid muscle, and a 0 and 2month immunization schedule, administering one dose of the active control vaccine (ShingrixTM) to the deltoid muscle. The trial results showed:

Adverse event rates in the high-dose group, low-dose group, placebo group, and active control group (ShingrixTM) were 30.00%、50.00%、20.00% and 100.00%, respectively.

The adverse event rate in both the experimental vaccine groups was similar to that in the placebo group, but significantly lower than in the active control group. The severity of adverse events was mainly Grade 1, requiring no treatment and resolving spontaneously.

Humoral Immunity: In both high-dose and low-dose groups, the seroconversion rate for anti-gE antibodies (ELISA) 1 month after full immunization was 100%, with antibody levels of 23.73 IU/mL and 24.84 IU/mL, respectively, representing a 16.88 and 34.04fold increase from baseline. The seroconversion rate for anti-VZV antibodies (FAMA) was also 100%, with geometric mean titers (GMT) of 512.00 and 194.01, respectively, reflecting a 36.76 and 13.93fold increase from baseline. The GMT for anti-VZV antibodies was significantly higher in the high-dose group compared to the low-dose group. There were no significant differences between the high-dose, low-dose groups, and the active control group in terms of the seroconversion rate, seroconversion

rate, or 2fold increase in anti-gE and anti-VZV antibodies.

Cellular Immunity: 30 days after full immunization, the proportion of gE-specific CD4+ and CD8+ T cells expressing two or more cytokines (IFN- γ , TNF- α , IL-2, and CD40L) was 85.00%、65.00%、20.00%、75.00%，and 70.00%、55.00%、25.00%、45.00%，and 45.00% in the high-dose, low-dose, placebo, and active control groups, respectively. Both the high-dose and low-dose experimental groups, as well as the active control group, showed significantly higher levels than the placebo group. There were no significant differences between the high-dose, low-dose experimental groups, and the active control group, although the high-dose test group exhibited a slight advantage.

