7.6 Immunogenicity Evaluation

Evaluable subjects (those meeting all inclusion criteria, adhering to protocol-defined procedures and intervals, and without any exclusion criteria) will have their immunogenicity assessed using data obtained from ELISA and flow cytometry. The immunogenicity metrics include seroconversion rate, anti-gE antibody GMC, geometric fold increase, and the proportion of VZV gE-specific CD4+/CD8+ T cells expressing at least two cytokines (TNF- α , IFN- γ , IL-2, CD40L), comparing post-vaccination results to baseline.

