8.2 Sample Size Determination

Assuming that, 30 days after full immunization, the proportion of gE-specific CD4+ T cell activation with two or more cytokines (IFN- γ , TNF- α , IL-2, CD40L) is 85% in the experimental vaccine group and 75% in the active control group, and the proportion of gE-specific CD8+ T cell activation with two or more cytokines is 55% in the experimental vaccine group and 45% in the active control group, with an assumed dropout rate of 10%, a sample size of 150 subjects per group will yield 135 evaluable subjects per group. At a one-sided significance level of 0.025, this sample size provides approximately 90% power to test the above non-inferiority hypothesis.

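### The primary cellular comparison leaves the Day-0 cellular result unused; adjusting for it is a free gain in precision, of possible value mainly for CD8

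*Protocol*

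**What the plan says.** Section 8.4.2 of the protocol fixes the primary analysis. For CD4+ and CD8+ separately it takes the proportion with at least two cytokines 30 days after the second dose, forms the difference between arms, and states that "its 95% confidence interval (using the Miettinen and Nurminen method) will also be calculated". Non-inferiority is concluded if the lower limit lies above -10%. No covariate, stratum or change from Day 0 is named.

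Four other places treat the Day-0 result as available and relevant:

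- Section 3.1.1.1: "Blood samples will be collected from all subjects once before vaccination and once 30 days after full immunization". Its table assigns 15 to 20 mL of the Day-0 draw to the cellular assay.
- Section 8.3: both the FAS and the PPS require a baseline immunogenicity result. The wording does not separate the antibody result from the cellular one.
- Section 7.6: the cellular proportion is listed among the metrics assessed by "comparing post-vaccination results to baseline".
- Section 8.4.3: the log post-vaccination antibody concentration is analysed with the log baseline concentration as covariate, and a fold rise is reported.

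**The concern.** Section 7.6 promises a comparison with baseline for the cellular metric, and the analysis in 8.4.2 does not make one. The two passages do not agree on how Day 0 enters the primary endpoint.

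The statistical cost is precision. If subjects who respond at Day 0 tend to respond after vaccination whichever vaccine they get, part of the variation in the primary endpoint is predictable from data already in hand. Leaving it out widens the interval and lets a chance difference between arms in Day-0 responders move the estimate. CD8 is where this could matter, because it is the test with the least power to spare. Section 5.5.2 describes 1:1 block randomisation and names no stratification factor, so nothing in the design balances Day-0 status beyond chance.

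**Working it through.** **Inputs from section 8.2.** CD4: the proportion "is 85% in the experimental vaccine group and 75% in the active control group". CD8: it "is 55% in the experimental vaccine group and 45% in the active control group". There are 135 evaluable subjects per arm, the test is one-sided at 0.025, and the margin is 10 points.

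**The plan's own power.** Power = Φ((d + 0.10)/SE - 1.96), with SE = √[(p₁(1-p₁) + p₂(1-p₂))/135].

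- CD4: SE = √(0.315/135) = 0.0483; 0.20/0.0483 - 1.96 = 2.18; power 98.5%.
- CD8: SE = √(0.495/135) = 0.0606; 0.20/0.0606 - 1.96 = 1.34; power 91.0%.
- Exact enumeration of the Miettinen-Nurminen test gives 98.5% and 91.1%.
- Both tests together: 89.7% if independent, and at least 89.6% by the Bonferroni bound.

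The stated "this sample size provides approximately 90% power to test the above non-inferiority hypothesis" therefore reproduces. The exact one-sided error of the unadjusted CD8 test at 35% vs 45% is 0.0242, so the test is valid.

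**Assumed inputs.** The protocol gives neither a Day-0 cellular response rate nor its correlation with the post-vaccination response. The only proxy is the Phase I placebo arm in section 3.2.3.1, 20% (CD4) and 25% (CD8), for "the proportion of gE-specific CD4+ and CD8+ T cells expressing two or more cytokines". These were measured after the injections, not at Day 0. The CD8 list has five values for four groups, so 25% is the value in the placebo position. I take prevalence q = 0.20 (CD4) and 0.25 (CD8), and let the share a of Day-0 responders who are positive after vaccination, equal in both arms, run from no association to 100%.

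**Precision gain.** In an arm with response rate p, the Day-0/post correlation is φ = q(a - p)/√[q(1-q)p(1-p)], and adjustment multiplies that arm's variance by 1 - φ². For CD8 with a = 0.80:

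- Experimental: φ = 0.0625/0.2154 = 0.290. Control: φ = 0.0875/0.2154 = 0.406.
- Variance sum = 0.2475(1 - 0.084) + 0.2475(1 - 0.165) = 0.433, against 0.495 unadjusted: 12% less.
- Power = Φ(0.20/√(0.433/135) - 1.96) = Φ(1.57) = 94.2%.

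| CD8, Day-0 responders still positive | Variance reduction | Power, 135 per arm | n per arm for 90% |
|---|---|---|---|
| no association | 0% | 91.0% | 131 |
| 70% | 6% | 92.5% | 123 |
| 80% | 12% | 94.2% | 114 |
| 90% | 22% | 96.2% | 102 |
| 100% | 34% | 98.2% | 86 |

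For CD4 the ceiling is a 7% variance reduction and power of 99.0%, a gain of 0.5 point. A simulation of a Day-0-stratified CD8 difference (40,000 trials) gave adjusted power of 0.908 at 55% retention, 0.942 at 80% and 0.980 at 99%. It used a simple Wald variance, whose one-sided error was 0.025 to 0.028.

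**Chance imbalance.** With q = 0.25, the SD of the between-arm difference in Day-0 responders is √(2 × 0.25 × 0.75/135) = 5.3 points. The average within-arm gap in post-vaccination response between Day-0 positives and negatives is 0.40 at 80% retention and 0.67 at 100%. A one-SD imbalance therefore shifts the unadjusted CD8 difference by about 2.1 to 3.5 points.

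**What the margin means among Day-0 negatives.** If every Day-0 responder stays positive in both arms, the overall difference is D = q × 0 + (1 - q) × D_neg, so D = -10 corresponds to D_neg = -10/(1 - q). This is -10.5 at q = 5%, -12.5 at 20%, -13.3 at 25% and -14.3 at 30%. A stratified or standardised overall difference averages the strata with the same weights, so the relation is unchanged by adjustment.

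**The case against.** The case for leaving 8.4.2 alone is that an unadjusted Miettinen-Nurminen difference is a legitimate prespecified non-inferiority analysis that holds its error rate and about meets its stated power. Its interval already allows for chance baseline imbalance, and a covariate model for a continuous antibody concentration does not oblige anyone to adjust a binary endpoint. All of this stands, and it is why the point is one of efficiency.

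The size is also uncertain. If the Phase I placebo positivity is unstable assay background, the Day-0/post correlation is near zero and so is the gain. The VZV seroprevalence above 90% in section 1.1 concerns IgG, not polyfunctional T cells. This stands too, so the range has to start at no gain.

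A reader might go further and infer that pre-existing responders dilute the -10 point margin and make non-inferiority easier to reach. The documents do not support that as a fact. It needs appreciable Day-0 positivity that persists in both arms and a response rule not relative to Day 0. The protocol gives no Day-0 rate and no cellular positivity rule; if response means a rise over Day 0, the argument largely falls away. Nor would adjustment cure it, since the overall estimand is unchanged.

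An unseen SAP may add supportive analyses. It would not remove the disagreement between 7.6 and 8.4.2, because the protocol itself fixes the primary method.

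**Conclusion.** Section 8.4.2 makes no use of a Day-0 cellular result that the trial collects from everyone and that 7.6 names as the comparator. This is a missed, cost-free improvement in precision. The primary test is neither invalid nor short of its stated power.

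At an assumed 25% Day-0 CD8 positivity, the gain in CD8 power runs from nil to about 7 points (91% to 98%), with about 3 points at 80% retention. CD4 gains at most half a point. Adjustment also takes the effect of chance Day-0 imbalance out of the estimate.

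Separately, and only if Day-0 responders stay positive in both arms and response is not defined relative to baseline, -10 points overall corresponds to about -10.5 to -14.3 points among Day-0 negatives for a prevalence of 5 to 30%. That is a question of interpretation which adjustment leaves open.

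**What to change.** - In 8.4.2, make the primary estimate a risk difference adjusted for the Day-0 cellular result, at the same -10% margin. Either use a Miettinen-Nurminen interval stratified by Day-0 status, applying the same positivity rule as after vaccination, or standardised logistic regression on log Day-0 frequency. Name the interval method, since the simple Wald version ran slightly above the nominal error.
- Keep the unadjusted difference as a sensitivity analysis.
- Reconcile 7.6 with 8.4.2, stating the subject-level response rule and whether it is relative to Day 0. The endpoint is worded as a proportion of T cells in 2.2.1 and of subjects in 3.1.3.1, and no threshold is given; stratifying by Day-0 status depends on this rule.
- Report the difference among Day-0 negatives as a supportive analysis.

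No extra visits, samples or subjects are needed. The cost is wording plus settling the positivity rule. It should be settled early: section 5.5.3.2 provides for unblinding before the second dose, and an adjustment chosen after that could look data-driven.

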8.4.3 Humoral Immunogenicity

Thirty days after full immunization, the anti-gE antibody concentration will undergo a logarithmic transformation, and an analysis of covariance model will be used to analyze the data. In this model, the logarithmic transformation of the antibody concentration at 30 days post-full immunization will be the dependent variable, the logarithmic transformation of the pre-immunization antibody concentration will be the covariate, and the group will be the fixed effect. Based on this model, the least squares mean of the log-transformed geometric mean concentration (GMC) of anti-gE antibodies at 30 days post-full immunization for each group and the between-group difference (experimental vaccine group - active control vaccine group) will be calculated. After

back-transformation, the GMC of anti-gE antibodies at 30 days post-full immunization for each group and their 95% confidence intervals, as well as the between-group ratio (experimental vaccine group / active control vaccine group) and its 95% confidence interval, will be computed.

The seroconversion rate of anti-gE antibodies at 30 days post-full immunization (defined as at least a fourfold increase in antibody levels post-immunization) will be calculated for both the experimental vaccine group and the active control vaccine group. The 95% confidence interval for each group rate will be calculated using the Clopper-Pearson method.

The geometric mean fold rise in anti-gE antibodies from pre-immunization (Day 0) to 30 days post-full immunization will be calculated for each group, along with its 95% confidence interval.

Reverse cumulative distribution plots of anti-gE antibody titers will be created separately for the experimental vaccine group and the active control vaccine group at pre-immunization and at 30 days post-full immunization.

Humoral immunogenicity analysis will primarily be based on the per-protocol set.

8.4.4 Safety

This study will primarily focus on the statistical analysis of treatment-emergent adverse events (TEAEs) occurring after vaccination. Adverse events occurring before vaccination will be listed separately. Unless otherwise specified, the term "adverse events" in the following sections refers to TEAEs.

Solicited adverse events occurring 0-7 days post-vaccination, as well as solicited adverse events related to vaccination, will be categorized and analyzed by group, type of reaction (systemic and local), and the severity of each solicited adverse event as listed in Section 3.1.3.2. For these events, the number of adverse events, the number of subjects experiencing them, and the incidence rate will be calculated.

The following adverse events will be categorized and analyzed by group, System Organ Class (SOC), and Preferred Term (PT), calculating the number of events, the number of affected subjects, and the incidence rate:

- Unsolicited adverse events occurring 0-30 days after each dose;
- Adverse events occurring within 30 minutes after each dose;
- All adverse events occurring 0-30 days after each dose;
- Adverse events of special interest occurring from the first dose to 30 days after full immunization;
- Serious adverse events occurring from the first dose to 6 months after full immunization.

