Secondary objective	To evaluate the immunogenicity and safety of humoral immune responses induced by recombinant zoster vaccine (CHO cells) in subjects aged 50 years and older.

Study Endpoints

Primary endpoints	The proportion of specific CD4+/CD8+ T cells activating at least two cytokines (TNF- α , IFN- γ , IL-2, CD40L) 30 days after full immunization.
Secondary endpoints	
Immunogenicity endpoints
 
 1. Geometric Mean Concentration (GMC) and seroconversion rate of anti-gE antibodies 30 days after full immunization; 2. Geometric Mean Fold Increase (GMFI) in anti-gE antibodies 30 days after the whole immunization course compared to pre-immunization (Day 0). 
Safety endpoints
 
 1. Incidence of solicited adverse events (AE) within 0-7 days after each dose, including local (injection site) and systemic (non-injection site) reactions; 2. Incidence of unsolicited AEs within 0-30 days after each dose; 3. Incidence of AEs within 30 minutes after each dose; 4. Incidence of adverse events of special interest (AESIs) from the first dose through 30 days after full immunization; 5. Incidence of serious adverse events (SAEs) from the first dose through 6 months after full immunization.

Study Design

Overall design	
Study design: Randomized, partially blinded
 
Immunization schedule: Experimental vaccine at 0 and 30 days; active control vaccine at 0 and 60 days

----------------	---

	
Study groups: Experimental group and control group
 
Blinding: LZ901-330 is a partially blinded study, with a double-blind design prior to the second dose, and an open-label design at the time of the second dose.
 
Number of subjects and groups
 
Approximately 300 subjects aged 50 and older will be enrolled and randomly assigned in a 1:1 ratio to the experimental group and the control group. The experimental group will receive two doses of the recombinant zoster vaccine (CHO cell), developed and manufactured by Beijing Luzhu Biotechnology Co., Ltd. / Luzhu Biopharmaceuticals (Zhuhai) Co., Ltd., with an immunization schedule of 0 and 30 days. The control group will receive two doses of the Recombinant Zoster Vaccine (RZV, ShingrixTM), products of GlaxoSmithKline Biologicals SA, with an immunization schedule of 0 and 60 days.
																							

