3.2 Rationale for the Selection of the Study Design

3.2.1 Rationale for the Selection of the Control Vaccine

ShingrixTM is a Herpes Zoster subunit vaccine developed by GlaxoSmithKline Biologicals (GSK). The vaccine consists of the VZV glycoprotein E (gE) and a special adjuvant. ShingrixTM in immunocompetent adults ≥ 50 years reduced the incidence of herpes zoster and PHN by 97.2% and 91.2%, respectively, and by 89.8% and 88.8% in elders ≥ 70 years, which showed better efficacy than live attenuated vaccine ZostavaxTM. However, the ultra-high incidence of side effects limits its promising application. In August 2020, this vaccine was officially launched in mainland China for the prevention of herpes zoster in individuals aged 50 and older. The vaccine is administered in a 50 μ g dose via intramuscular injection into the deltoid muscle, with two doses given 1 to 6 months apart.

The herpes zoster subunit vaccine developed by GlaxoSmithKline Biologicals SA (CHO cells) (brand name: ShingrixTM), which is already available on the market in China, has been selected as the active control to evaluate the immunogenicity and safety of the experimental vaccine. The experimental vaccine will follow a 0-30day immunization schedule with two doses, while the control vaccine will follow a 0-60day schedule with two doses. Both the experimental vaccine and the control vaccine will have a dose of 0.5 mL per administration.

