5.1.7 The second dose of vaccination

The experimental group will receive two dose recombinant zoster vaccine (CHO cells) developed by Beijing Luzhu Biotechnology Co., Ltd./Luzhu Biopharmaceuticals (Zhuhai) Co., Ltd., following a 0 and 30-day immunization schedule.

The control group will receive the two dose Recombinant Zoster Vaccine (RZV, ShingrixTM) developed by GlaxoSmithKline Biologicals SA, following a 0 and 60-day immunization schedule.

Subjects in the experimental group will receive the second dose on Day 30, with a window period of -2/+7 days.

Subjects in the control group will receive the second dose on Day 60, with a window period of -2/+7 days.

If a subject has a relative or absolute contraindication, the vaccination schedule may be postponed or interrupted as described in Section 6.1.1.

Both the experimental and control vaccines will be administered via intramuscular

Group	Study Intervention	Dose	Vaccination Time		
			D0	D30	D60
experimental group	experimental vaccine	0.5mL/dose	√	√	—
control group	control vaccine	0.5mL/dose	√	—	√

injection into the deltoid muscle. The dose and schedule are as follows:

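### AESI and SAE incidence is tabulated by group over windows of unequal nominal length (60 vs 90 days and 210 vs 240 days), so the two arms are not shown like for like

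*Protocol*

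**What the plan says.** The schedules differ by design. The Protocol Synopsis (Study Design) gives "Experimental vaccine at 0 and 30 days; active control vaccine at 0 and 60 days". Section 5.1.7 repeats this with visit windows: "Subjects in the experimental group will receive the second dose on Day 30, with a window period of -2/+7 days" and "Subjects in the control group will receive the second dose on Day 60, with a window period of -2/+7 days".

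Two safety endpoints in Section 2.2.2 end at a time counted from full immunization, and Section 8.4.4 carries them into the analysis: "Adverse events of special interest occurring from the first dose to 30 days after full immunization" and "Serious adverse events occurring from the first dose to 6 months after full immunization". Both are summarised by group, system organ class and preferred term, "calculating the number of events, the number of affected subjects, and the incidence rate". Section 8.4.4 states no common window and no person-time denominator.

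The remaining safety endpoints (30 minutes, 0–7 days, 0–30 days) are counted from each dose, so they have the same nominal length in both arms. Section 3.2.1 says that the control "has been selected as the active control to evaluate the immunogenicity and safety of the experimental vaccine".

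**The concern.** When follow-up ends a fixed time after dose 2, and dose 2 comes 30 days later in one arm, that arm is watched for 30 more days. Background events in those days are counted for the control and have no counterpart for LZ901. A reader who sets the two incidences side by side, as the study title and Section 3.2.1 invite, sees a difference that comes partly from the length of observation. If capture is complete, the direction favours LZ901.

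Surveillance inside the longer window also differs. In the Schedule of Activities the first Contact Card is collected from everyone at Day 30. Controls receive a Diary Card at Day 60 and their next Contact Card at Day 67. They therefore hold no card from Day 30 to Day 60, which are the days that lengthen their AESI window.

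**Working it through.** **Inputs from the protocol**
- Dose 2: Day 30 (LZ901) and Day 60 (control), Section 5.1.7.
- One month = 30 days, Definitions of Terms; so 6 months = 180 days.
- Group size 150, Sections 3.1 and 8.2.
- Herpes zoster incidence 5 per 1000 per year at age 50–59 and 10 per 1000 per year at 60 and over, Section 1.1.

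**Assumed, because the protocol gives no figure**
- SAE rate 20 to 200 per 1000 person-years.
- A suspected-zoster rate of 200 per 1000 person-years, as an illustration only. The definition is broad: any one of its criteria is enough, including unilateral pain or rash, or neuralgia.

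**1. Window length = day of dose 2 + follow-up after dose 2**

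| | LZ901 | Control | LZ901/control |
|---|---|---|---|
| AESI | 30 + 30 = 60 days | 60 + 30 = 90 days | 60/90 = 0.67 |
| SAE | 30 + 180 = 210 days | 60 + 180 = 240 days | 210/240 = 0.875 |

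Check against the plan's own figure: 210/30 = 7.0 months and 240/30 = 8.0 months. This reproduces the participation of about 7 to 8 months in the Synopsis and Section 3.1.4.

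**2. Expected affected subjects per 150, same constant hazard in both arms, complete capture**

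Formula: 150 × [1 − exp(−rate × days/365)], with the rate per person-year.

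| Rate per 1000 person-years | LZ901 | Control | Difference |
|---|---|---|---|
| Zoster 5 (protocol) | 0.12 | 0.18 | 0.06 |
| Zoster 10 (protocol) | 0.25 | 0.37 | 0.12 |
| Suspected zoster 200 (assumed) | 4.85 | 7.22 | 2.37 |
| SAE 20 (assumed) | 1.72 | 1.96 | 0.24 |
| SAE 100 (assumed) | 8.39 | 9.55 | 1.16 |
| SAE 200 (assumed) | 16.30 | 18.48 | 2.18 |

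**3. Would it produce a nominal finding?** By a normal approximation, the chance of a two-sided 5% result with the control higher is about 3% to 6% over the SAE range, and 3% to 4% for AESIs at the protocol's zoster rates. With equal windows it would be 2.5% in that direction. The approximation is rough at such small counts.

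**4. Effect of the card gap.** Any AESI missed between Day 30 and Day 60 lowers the control count and moves the ratio from 0.67 towards 1. If nothing were captured in those 30 days, the effective windows would be 60 and 60 days and the ratio 1.00. The true value lies between, and the protocol gives nothing to place it. SAEs are much less affected: they are asked about at the Day 30 and Day 60 visits for all subjects, and Section 5.1.9.1 adds self-report and periodic telephone follow-up.

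**5. After the change.** AESIs over 30 days after each dose: 60 vs 60 days. SAEs over 30 days after dose 1 plus 180 days after dose 2: 210 vs 210 days. Both expected ratios are then 1.00.

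**The case against.** The strongest reply is that no safety comparison is planned. Section 8.4.4 tabulates by group and gives no test, difference, ratio or interval, unlike Sections 8.4.2 and 8.4.3. The secondary objective does not set safety against the control in so many words, and exposure adjustment is often left to an analysis plan. Section 8.4.4 also tabulates all AEs over 0–30 days after each dose, so an AESI or SAE with onset in those days already appears in a table of equal length. These points stand, and they keep this a descriptive matter. They do not remove it: the two windows are fixed as endpoints in the protocol itself, and Section 3.2.1 gives the control a role in evaluating safety.

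A reader might infer that equally safe vaccines would be shown to differ. The documents do not support that. Reactions that cluster in the 30 days after each dose are counted equally in both arms; only background events in the extra inter-dose days are affected, and the shift is small beside chance variation.

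A reader might also take 0.67 as the expected AESI ratio. It holds only under complete capture, and the card gap works against it.

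Finally, a cut-off at Day 210 in both arms may look like the simple cure for SAEs. It would leave controls 210 − 60 = 150 days after dose 2 against 180 for LZ901. It would not be reached by everyone either: dose 2 at Day 28 with the last visit 7 days early ends LZ901 follow-up at 28 + 173 = Day 201.

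**Conclusion.** The point holds in a limited form. As written, AESI and SAE incidences rest on nominal windows of 60 vs 90 and 210 vs 240 days, and should not be read side by side as like for like. Under equal constant background hazards the expected LZ901/control ratio is 0.875 for SAEs, given complete capture, and between about 0.67 and 1 for AESIs, depending on capture between Day 30 and Day 60.

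In absolute terms this is about 0.1 subject per 150 for zoster at the protocol's rates and roughly 0.2 to 2 subjects for SAEs over the assumed range. It would reach more than two subjects for AESIs only if the broad suspected-case definition produced a much higher rate, for which the protocol gives no figure. The primary endpoint and the dose-anchored safety endpoints are untouched. The correction is worth making because it uses data already collected.

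**What to change.** In Sections 2.2.2 and 8.4.4 (and the Synopsis endpoints), base the between-group summary on:
- **AESIs:** 0–30 days after each dose, 60 vs 60 days.
- **SAEs:** 30 days after dose 1 plus 180 days after dose 2, 210 vs 210 days, counting each calendar day once. Alternatively, give events per person-time with an exact confidence interval for the rate ratio.

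The dose-anchored form makes no constant-hazard assumption for dose-related events. If every SAE were dose-related and the counts equal, a person-time rate ratio would be 240/210 = 1.14 against LZ901, the opposite distortion. Early last visits shorten the dose-anchored window in the same way in both arms.

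Keep the windows as now written in supplementary tables or listings, so that no event is lost from view.

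Reconcile the AESI window itself. The safety observation text in the Synopsis and in Section 3.1.3.2 can be read as ending at full immunization, whereas Sections 2.2.2, 5.1.9.2, 7.4.7 and 8.4.4 run to 30 days after it.

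**Cost:** no new visits or data. Control events between Day 31 and dose 2 leave the main comparison unless person-time is used. Because endpoint wording changes, a minor protocol amendment with ethics submission under Section 10.1.4 is needed.
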